2.13 Interim analysis

2.13.1 Disease free survival (DFS)

One interim analysis is planned after approximately 196 of the approximately 392 targeted DFS events, i.e., at approximately 50% information fraction, respectively, has been documented. The primary intent of the interim analysis is to stop early for lack of efficacy (futility). There is no intent to carry out an analysis to declare superior efficacy at the time of the first interim analysis.

An α -spending function according to a 2-look Lan-DeMets group sequential design with O'Brien-Fleming type stopping boundary will be used to construct the efficacy stopping boundaries ([Lan and DeMets 1983](#)). A user-defined gamma function with $\gamma = -3$ stopping boundary will be used as a β -spending function to determine the non-binding futility boundary. The choice of non-binding nature of the futility stopping boundary ensures that the efficacy stopping boundaries are not affected. Based on the choice of α -spending and β -spending function described above and if the interim analysis is performed *exactly* at 196 DFS events, the futility boundary expressed on p -value (or Z -statistic) at the first interim is calculated as 0.411 (or 0.226), i.e., the observed p -value has to be greater than 0.411 (or calculated Z -statistic is < 0.226) to conclude futility.

Since the observed number of events at the interim analysis may not be exactly equal to the planned 196 DFS events, the futility boundaries will need to be recalculated based on the *exact* information fraction. The observed p -value (or Z -test statistic) at the interim analyses will then be compared against the re-calculated futility boundary.

If the study continues to the final DFS analysis, the final DFS analysis will be performed when *approximately* 392 DFS events have been documented. If exactly 196 events are observed at the interim analysis, exactly 392 events are obtained at the final analysis, the observed p -value will have to be less than 0.024 (or the observed Z statistics has to be > 1.969) to declare statistical significance. With consideration of the p -value has been spent at interim analyses, in practice, the boundary for the final analysis will be derived accordingly from the pre-specified α -spending function such that the overall significance level across all analyses is maintained at 0.025.

Since the planned efficacy interim analysis was not performed, the efficacy boundary and observed p -value at the final DFS analysis will take into account only the interim analysis actually performed (i.e. futility analysis). The statistical properties of the group sequential design are summarized for DFS in [Table 2-9](#) below.

Table 2-9 Simulated probabilities to stop for futility or efficacy at the interim or final DFS analysis

Scenario	Look	# DFS events	Simulated cumulative probabilities (%)		Simulated incremental probabilities (%)	
			Stop for efficacy	Stop for futility	Stop for efficacy	Stop for futility
Under H_{01} (HR=1)	1st IA (futility)	196	-	59.34	-	59.34
	Final	392	2.36	-	2.18	-
Under H_{a1} (HR=0.716)	1st IA (futility)	196	-	1.83	-	1.83
	Final	392	89.56	-	63.7	-
Under HR=0.8	1st IA (futility)	196	-	9.28	-	9.28
	Final	392	58.65	-	50.49	-

Note: Simulation is performed in East 6.4 with number of simulations = 10,000 and randomization seed = 1234

The interim analysis will be performed by an independent statistician (not involved with the conduct of the study). Further details are described in the DMC charter. The results of the interim analyses will be provided to the DMC by the independent statistician.

2.13.2 Key secondary endpoint: Overall survival (OS)

A hierarchical testing procedure will be adopted and the statistical tests for OS will be performed only if the primary efficacy endpoint DFS is statistically significant.

A maximum of three analyses is planned for OS; at the time of final analysis for DFS provided DFS is significant, at which point a total of approximately 318 (63%) deaths are expected, an additional IA for OS when a total of approximately 418 (83%) deaths are expected, and a final analysis for OS when approximately 504 deaths are expected.

A α -spending function according to Lan-DeMets ([Lan and DeMets 1983](#)) (O'Brien-Fleming) α -spending function along with the testing strategy outlined below will be used to maintain the overall type I error probability. This guarantees the protection of the 2.5% overall level of significance across the two hypotheses and the repeated testing of the OS hypotheses in the interims and the final analysis ([Glimm 2010](#)).

The trial allows for the stopping of the study for a superior OS result, provided the primary endpoint DFS has already been shown to be statistically significant favoring the test treatment arm. Further, the

exact nominal p -values that will need to be observed to declare statistical significance at the time of these analyses for OS will depend on the number of OS events that have been observed at the time of these analyses and the α for OS already spent at the time of earlier analyses.

Unblinded results from the interim analysis for DFS will not be communicated to the Sponsor's clinical team or to any party involved in the study conduct (apart from the independent statistician and DMC members) until the DMC has determined that either i) DFS analysis has crossed the pre-specified boundary for efficacy, or ii) DMC determines if the study needs to be terminated due to any cause including futility or safety reasons. Further details will be described in the DMC Charter. At the time of final DFS analysis, both DFS and interim OS analysis will be performed by the Sponsor's clinical team. Investigators and subjects will remain blinded to study treatment and all subjects will continue to be followed for OS until the final OS analysis (or earlier if OS reaches statistical significance at any of the interim analyses).

The statistical properties of the group sequential design are summarized for OS in [Table 10-2](#) below.

Table 2-3 Simulated cumulative power to stop for efficacy on overall survival at final DFS analysis or final OS analysis

Look	Months after randomization of the first subject (approximation)	# DFS Events	Cumulative power against a hazard ratio of 0.716	# OS Events	Cumulative power ^b against a hazard ratio of 0.776
1st DFS IA (futility)	27	196 (50.0%)	-	-	-
Final DFS	42	392 (100%)	89.56%	318 (63.1%) ^a	36.26%
OS IA	52	-	-	418 (82.9%) ^a	64.09%
Final OS	63	-	-	504 (100%) ^a	79.25%

a: To be performed only if the final DFS analysis is significant

b: Power conditional on DFS being significant

Simulations performed in East 6.4 with number of simulations = 10,000 and randomization seed =1234.

2.13.3 Confidentiality of interim results

At the time of the interim analysis for DFS, interim analysis will be performed by an independent statistician. Analysis results from the interim analysis for DFS will not be communicated to the sponsor's clinical team or to any party involved in the study conduct until the DMC has determined that the study needs to be terminated due to any cause including futility or safety reasons. Further details will be described in the DMC Charter.

At the time of final DFS analysis, both DFS and interim OS analysis will be performed by the sponsor's clinical team. All subjects will continue to be followed for OS until the final OS analysis or earlier if OS reaches statistical significance at any of the interim analyses. Any subsequent OS interim analysis and final OS analysis will also be performed by the Sponsor's clinical team.

3 Sample size calculation

3.1 Primary analysis

The sample size calculation is based on the primary variable DFS. The hypotheses to be tested and details of the testing strategy are described in [Sections 2.5.2](#).

Based on available data, the median DFS in the placebo arm is around 48 months ([Kelly 2015](#)). It is expected that treatment with canakinumab will result in a 28.4% reduction in the hazard rate for DFS (corresponding to an increase in median DFS from 48 months to 67 months under the exponential model assumption).

Then, in order to ensure 90% power to test the null hypothesis: DFS hazard ratio = 1, versus the specific alternative hypothesis: DFS hazard ratio = 0.716, it is calculated that a total of 392 DFS events need to be observed. This calculation assumes analysis by a one-sided log-rank test at the overall 2.5% level of significance, subjects randomized to the two treatment arms in a 1:1 ratio, and a 2-look group sequential design with a Lan-DeMets (O'Brien-Fleming) α -spending function and a user-defined gamma function with $\gamma = -3$ to define a non-binding futility rule at the interim analysis, using an information fraction of 50% for the interim analysis (futility only). Assuming that enrolment will continue for approximately 30 months at a rate of 50 subjects per month and a 5% annual dropout rate by the time of the final DFS analysis, a total of approximate 1500 subjects will need to be randomized to observe the targeted 392 DFS events at about 12 months after the randomization date of the last subject, i.e., 42 months after the randomization date of the first subject. These calculations were made using the software package East 6.4.

The final DFS analysis is planned to be performed when *approximately* 392 DFS events are documented to ensure the trial is not over-powered. At the time of the data cut-off for final DFS analysis, all subjects randomized prior to the data cut-off date for final DFS analysis who have had at least one post baseline recurrence assessment (i.e. all subjects have a minimal follow-up of 3 months) or discontinued study earlier will be included.

3.2 Power for analysis of key secondary variables

OS, as the key secondary variable, will be formally statistically tested, provided that the primary variable DFS is statistically significant. The hypotheses to be tested and details of the testing strategy are provided in [Section 2.6.2](#). Based on available data, the median OS in the placebo arm is expected to be approximately 5 years ([Pignon 2008](#)). In addition, the OS result presented in ([Kelly 2015](#)) was not mature as the median was not reached at 5 years, but the overall trend indicates a median OS greater than 5 years. After taking these into consideration, the median OS for the placebo arm is assumed to be approximately 66 months. It is hypothesized that treatment with canakinumab will result in a 22.4% reduction in the hazard rate for OS, i.e., an expected hazard ratio of 0.776. It corresponds to an increase in median 66 to 85 months under the exponential model assumption. Then, in order to ensure 80% power to test the null hypothesis: OS hazard ratio = 1, versus the specific alternative hypothesis: OS hazard ratio = 0.776, it is calculated that a total of 504 deaths need to be observed. This calculation assumes analysis by a one-sided log-rank test at the overall 2.5% level of significance, subjects randomized to the two treatment arms in a 1:1 ratio, and a group sequential design with a Lan-DeMets α -spending function using information fractions according to actual events observed at performed analysis time points. All the efficacy boundaries will be calculated based on actual events and the number of interim analyses.

4 Change to protocol specified analyses

Not applicable

5 Appendix

This will be used later for drafting CSR Appendix 16.1.9.

5.1 Imputation rules

5.1.1 Study treatment

No imputation of the start date of infusion or end date for infusion will be applied. Complete dates are required as per eCRF.

5.1.2 AE, ConMeds and safety assessment date imputation

Table 5-1 Imputation of start dates (AE, CM) and assessments (LB, EG, VS)

Missing Element	Rule
day, month, and year	
 No imputation will be done for completely missing dates
day, month	
 If available year = year of study treatment start date then If stop date contains a full date and stop date is earlier than study treatment start date then set start date = 01JanYYYY Else set start date = study treatment start date. If available year > year of study treatment start date then 01JanYYYY If available year < year of study treatment start date then 01JulYYYY
day	
 If available month and year = month and year of study treatment start date then 
 If stop date contains a full date and stop date is earlier than study treatment start date then set start date= 01MONYYYY. Else set start date = study treatment start date. If available month and year > month and year of study treatment start date then 01MONYYYY If available month and year < month year of study treatment start date then 15MONYYYY

Table 5-2 Imputation of end dates (AE, CM)

Missing Element	Rule (* = last treatment date plus 130 days not > (death date, cut-off date, withdrawal of consent date))
day, month, and year	
 Completely missing end dates (incl. ongoing events) will be imputed by the end date of the on-treatment period*
day, month	
 If partial end date contains year only, set end date = earliest of 31DecYYYY or end date of the on-treatment period *
day	
 If partial end date contains month and year, set end date = earliest of last day of the month or end date of the on-treatment period*

Any AEs and ConMeds with partial/missing dates will be displayed as such in the data listings.

Any AEs and ConMeds which are continuing as per data cut-off will be shown as ‘ongoing’ rather than the end date provided.

5.1.2.1 Other imputations

Not applicable

5.2 AEs coding/grading

Adverse events are coded using the Medical dictionary for regulatory activities (MedDRA) terminology.

AEs will be assessed according to the Common Terminology Criteria for Adverse Events (CTCAE) version 5.0.

The CTCAE represents a comprehensive grading system for reporting the acute and late effects of cancer treatments. CTCAE grading is by definition a 5-point scale generally corresponding to mild, moderate, severe, life threatening, and death. This grading system inherently places a value on the importance of an event, although there is not necessarily proportionality among grades (a grade 2 is not necessarily twice as bad as a grade 1).

5.3 Laboratory parameters derivations

Grade categorization of lab values will be assigned programmatically as per NCI Common Terminology Criteria for Adverse Events (CTCAE) version 5.0. The calculation of CTCAE grades will be based on the observed laboratory values only, clinical assessments will not be taken into account. The criteria to assign CTCAE grades are given in Novartis internal criteria for CTCAE grading of laboratory parameters. The latest available version of the document based on the underlying CTCAE version 5.0 at the time of analysis will be used. For laboratory tests where grades are not defined by CTCAE version 5.0, results will be graded by the low/normal/high (or other project-specific ranges, if more suitable) classifications based on laboratory normal ranges.

A severity grade of 0 will be assigned for all non-missing lab values not graded as 1 or higher. Grade 5 will not be used. For laboratory tests that are graded for both low and high values, summaries will be done separately and labelled by direction, e.g., sodium will be summarized as hyponatremia and hypernatremia.

5.3.1 Imputation Rules

CTC grading for blood differentials is based on absolute values. However, this data may not be reported as absolute counts but rather as percentage of WBC.

If laboratory values are provided as ‘<X’ (i.e. below limit of detection) or ‘>X’, prior to conversion of laboratory values to SI unit, these numeric values are set to X.

The following rules will be applied to derive the WBC differential counts when only percentages are available for an xxx differential

$$\text{xxx count} = (\text{WBC count}) * (\text{xxx \%value} / 100)$$

Further derivation of laboratory parameters might be required for CTCAE grading. For instance, corrected calcium can be derived using the reported total calcium value and albumin at the same assessment using the following formula:

$$\text{Corrected Calcium (mmol/L)} = \text{Calcium (mmol/L)} + 0.020 [40 - \text{albumin (g/L)}]$$

In order to apply the above formula, albumin values in g/L will be converted to g/dL by multiplying by 0.1), calcium values in mmol/L will be converted to mg/dL by dividing by 0.2495. For calculation of laboratory CTC grades 0 and 1, the normal range for derived corrected calcium is set to the same limits (in mg/dL) as for calcium.

CTC grades for the derived absolute WBC differential counts (neutrophils, lymphocytes) and corrected calcium will be assigned as described above for grading

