	Section 3.1	Specified that the efficacy DFS IA was not performed and final DFS analysis is planned to be performed when approximately 392 DFS events are documented irrespective of the accrued sample size (even if less than 1500 subjects) to ensure the trial is not over-powered.

Date	Section	Changes
	Section 3.2	Specified that the OS efficacy boundaries will be calculated based on actual events and the number of interim analyses that are actually performed.
	Section 5.3	The formula for corrected calcium was updated: Corrected Calcium (mmol/L) = Calcium (mmol/L) + 0.020 [40 - albumin (g/L)]
	Section 6	All uncited references have been removed
21-Mar-2022	Rationale	In line with the protocol amendment 03 (03-Feb-2022), the purpose of this amendment is to remove the second interim analysis for DFS; include the comparison between the canakinumab and placebo arms of DFS and OS in subgroups defined by PD-L1 and CD8 expression as secondary endpoints; add PRO related endpoints: time to first 10 point deterioration for pain, cough and dyspnea per QLQ-LC13; time to first 10 point deterioration for global health status/QoL, shortness of breath, pain, role functioning, physical functioning and fatigue per QLQ-C30; time to 10 point definitive deterioration for role functioning, physical functioning and fatigue per QLQ-C30
	Section 1	Specified the SAP is based on the protocol amendment 03 (03-Feb-2022) and the primary CSR will be based on the final DFS analysis
	Section 1.1	Modified the study design by removing the second DFS interim analysis and the first OS interim analysis originally planned
	Section 1.2	Updated the study objectives and endpoints by adding two biomarker endpoints: DFS and OS in PD-L1 and CD8 subgroup; time to first 10 point deterioration for pain, cough and dyspnea per QLQ-LC13; time to first 10 point deterioration for global health status/QoL, shortness of breath, pain, role functioning, physical functioning and fatigue per QLQ-C30; time to 10 point definitive deterioration for role functioning, physical functioning and fatigue per QLQ-C30; [REDACTED]
	Section 2.2.1	Added PK and immunogenicity for Japanese subgroup analysis; non-Japanese subgroup analysis and removed Chinese subgroup analysis since a dedicated SAP will address it Added subgroups of PD-L1 categories (<1%, >= 1 %, < 50%, >= 50%, >= 1 % and < 49%) and CD8 categories by median or quartile (including its complements) for both efficacy and safety

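### The corrected-calcium rule puts g/dL and mg/dL values into a formula whose constants hold only in SI units, adding about 0.7 mg/dL at normal albumin and misgrading calcium

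*SAP*

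**What the plan says.** SAP section 5.3.1 says that "corrected calcium can be derived using the reported total calcium value and albumin at the same assessment", and gives the formula with a unit on every term:

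corrected calcium (mmol/L) = calcium (mmol/L) + 0.020 × [40 − albumin (g/L)]

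The Document History entry of 07-Jan-2022 records the same formula. The text after the formula reads "In order to apply the above formula, albumin values in g/L will be converted to g/dL by multiplying by 0.1", and continues that "calcium values in mmol/L will be converted to mg/dL by dividing by 0.2495". For grades 0 and 1, "the normal range for derived corrected calcium is set to the same limits (in mg/dL) as for calcium". CTC grades for "corrected calcium will be assigned as described above for grading".

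Section 5.3 makes the grading programmatic, from observed values without clinical assessment, and refers elsewhere for the cut-offs: "The criteria to assign CTCAE grades are given in Novartis internal criteria for CTCAE grading of laboratory parameters". Section 2.8.3 uses the grades in the worst post-baseline table, the baseline-to-worst shift tables (low and high directions separately) and the listing of grade 3 or 4 values. The close-out SAP repeats the chemistry grade table (Table 2-20, Table 12-14 in the primary CSR) and the grade 3 or 4 listing (Listing 14.3.4-1.1).

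**The concern.** A formula with dimensional constants holds only in the units for which those constants were set. Here the SAP makes conversion to other units a condition of applying the formula, not a step for presenting the result, and leaves the constants unchanged. A programmer who follows the text in order will subtract albumin in g/dL from a reference value in g/L, then add the result to calcium in mg/dL.

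The outcome would be an almost constant upward shift that no longer corrects for albumin, compared with normal limits that have not moved. Because the grading is programmatic, no clinical reading would catch it. Protocol Table 7-5 schedules albumin-corrected calcium as a laboratory test only at screening, so later corrected values would have to come from this derivation. At stake are the calcium rows of the safety laboratory tables and listings.

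**Working it through.** **Inputs from SAP section 5.3.1.** Constants 0.020 and 40; albumin in g/dL = 0.1 × albumin in g/L; calcium in mg/dL = calcium in mmol/L ÷ 0.2495. The plan states no numerical result to reproduce.

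**Is the formula coherent in its own units?** The slope is 0.020 mmol/L per g/L. In conventional units this is 0.020 ÷ 0.2495 × 10 = 0.80 mg/dL per g/dL. The correction is zero at 40 g/L, that is 4.0 g/dL. So the SI formula is coherent, and its mg/dL equivalent needs the constants 0.80 and 4.0, which the SAP does not give.

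**The two calculations, with A = albumin in g/L, as the amount added in mg/dL:**

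- SI formula, result converted: 0.020 × (40 − A) ÷ 0.2495
- As written, inputs converted: 0.020 × (40 − 0.1 × A)

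| Albumin (g/L) | SI formula | As written | Error |
|---|---|---|---|
| 20 | +1.60 | +0.76 | −0.84 |
| 25 | +1.20 | +0.75 | −0.45 |
| 30 | +0.80 | +0.74 | −0.06 |
| 35 | +0.40 | +0.73 | +0.33 |
| 40 | 0.00 | +0.72 | +0.72 |
| 45 | −0.40 | +0.71 | +1.11 |
| 50 | −0.80 | +0.70 | +1.50 |

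The written rule moves only from +0.76 to +0.70 over the whole range; its slope is 0.02 mg/dL per g/dL instead of 0.80. The error changes sign where the two are equal: A = (0.80 ÷ 0.2495 − 0.80) ÷ (0.020 ÷ 0.2495 − 0.002) = 30.8 g/L.

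**Single values at albumin 40 g/L:**

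- Calcium 2.50 mmol/L: 2.50 ÷ 0.2495 = 10.02 mg/dL; as written, 10.74.
- Calcium 2.00 mmol/L: 2.00 ÷ 0.2495 = 8.02 mg/dL; as written, 8.74.

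With assumed limits of 8.5 and 10.5 mg/dL, the first changes from normal to high and the second from low to normal.

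**Illustration on a population.** The documents give no calcium or albumin distribution and no limits. Assume calcium with mean 2.34 and SD 0.12 mmol/L, albumin with mean 41 and SD 4 g/L, both normal, and limits 8.5 to 10.5 mg/dL (2.121 to 2.620 mmol/L).

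- SI formula: mean 2.34 + 0.020 × (40 − 41) = 2.32 mmol/L; variance 0.12² + 0.08² − 2r × 0.12 × 0.08, where r is the calcium–albumin correlation and 0.08 = 0.020 × 4.
- As written: mean 2.34 ÷ 0.2495 + 0.020 × (40 − 4.1) = 10.10 mg/dL; SD close to 0.12 ÷ 0.2495 = 0.48, almost independent of r.

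| Assumed r | SI: high | SI: low | As written: high | As written: low |
|---|---|---|---|---|
| 0 | 1.9% | 8.3% | about 20% | about 0.05% |
| 0.3 | 0.7% | 5.2% | about 20% | under 0.1% |
| 0.5 | 0.2% | 3.0% | about 20% | under 0.1% |

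The direction is the same at each correlation. The percentages are specific to these assumptions.

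**The case against.** The strongest reply is that the section contradicts itself and is not wrong on every reading. The formula labels each term in SI units, and the same section speaks elsewhere of converting laboratory values to SI units, so a careful programmer could ignore the conversion sentence and get the right answer. The formula was updated on 07-Jan-2022, so that sentence may be left over from an older formula; this is inference. The derivation is also optional in wording and the grading criteria sit in a sponsor document that is not available here.

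It is right that the misgrading occurs only if the text is coded as it stands, and that the count of affected values is unknown. But the sentence says it is needed to apply the formula, and a plan should not rely on the programmer to overrule it.

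Three further points stand as limits. The error reverses below about 30.8 g/L. The population percentages rest on assumed distributions and depend on the correlation. The scope is narrow: calcium is not an adverse event of special interest and has no row in the protocol's Table 6-2, both arms get the same rule, and no efficacy test is touched.

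**Conclusion.** The concern holds: the rule is wrong as written. An SI formula is applied to inputs in g/dL and mg/dL with its constants unchanged. The error is +0.72 mg/dL at albumin 40 g/L, and ranges from +0.33 at 35 g/L to +1.50 at 50 g/L. These figures follow from the SAP's own constants and need no outside assumption. Above about 30.8 g/L the rule raises corrected calcium, so it creates false high grades and hides low ones; below that it under-corrects.

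A shift of this size against unchanged limits must move values that lie near a limit. How many cannot be stated from the documents; under the assumptions shown, high values go from between 0.2% and 1.9% to about 20%. The consequence is confined to descriptive calcium safety outputs, so this should be corrected but does not bear on the trial's efficacy conclusions.

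**What to change.** In SAP section 5.3.1, remove the sentence that converts the inputs, and compute corrected calcium with calcium in mmol/L and albumin in g/L as the formula states. Then do one of two things: divide the corrected result by 0.2495 and keep the existing sentence on mg/dL limits, or grade in mmol/L and reword that sentence to match. If conventional units are wanted throughout, state the equivalent constants, 0.80 mg/dL per g/dL with reference 4.0 g/dL.

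Check the derivation program behind the primary CSR and close-out outputs. If the inputs were converted as written, rerun the calcium rows of the chemistry grade and shift tables and the grade 3 or 4 listing. The cost is one or two sentences and a check of one derivation, plus the rerun if it is needed. There is no statistical downside.
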